# **Atraumatic versus Silver-Modified Atraumatic Restorative Treatment in Primary Molars: A Randomized Trial on Minimally Invasive Caries Management and Oral Health-Related Quality of Life**

## **Introduction:**

Early childhood caries (ECC) is a term that describes the presence of one or more decayed (cavitated and non cavitated lesions), missed (due to caries), or filled teeth in a child's primary dentition before the age of six (American Academy of Pediatric Dentistry, 2016).

The American Academy of Pediatric Dentistry (AAPD) adopted the term ECC to better reflect its multi-factorial and complex etiology including biological, socioeconomic, and behavioral factors (Tinatof, et al 2017).

Although the initiating biological key factors including cariogenic bacteria, fermentable carbohydrates, and susceptible tooth surfaces are the same for both adults and children, some epidemiological studies have also documented some environmental factors as low socioeconomic status, minority status, in addition to feeding practices and vertical bacterial transmission from the mother to the child as risk factors for ECC (Anil & Anand, 2017).

According to WHO, ECC is one of the most common childhood diseases affecting 60-90% of children worldwide. (WHO, 2016). In developed countries, the ECC prevalence is estimated to range from 1 to 12%, whereas it rises to 70% among some disadvantaged groups in these countries (Anil & Anand, 2017).

In developing countries, ECC has been a significant problem in many areas and its prevalence varies from one population to another, where it has reached up to 85% in some developing areas in Far East Asia (Shrestha et al., 2021).

Reports on the prevalence of early childhood caries have been reported in many countries worldwide including the Middle East region: In Jordan for example, a study was done by Rajab and Abdullah (2020) on 1557 children, showed that the prevalence of ECC was 72.5%, and 77.2% among 4 and 5 years old respectively (Rajab & Abdullah, 2020). In the

United Arab Emirates, a study was conducted by Alkhayat (2018), reported that ECC prevalence in 3, 4 and 5-years old children was 25.6%, 36.8%, and 42.2%, respectively among 2957 participants (Alkhayat, 2018). In Lebanon, a study was done by (Chedid et al., 2011) on a small sample of Lebanese preschool children aged below 4 years, and found that 75% of 99 children suffered from ECC (Chedid et al., 2011).

Caries may have a negative impact on oral health-related quality of life in preschool children. Oral health-related quality of life (OHRQoL) is a multidimensional concept that consists of subjective evaluations of oral health, functional and emotional well-being, satisfaction with care, and sense of self (Ruff et al., 2022).

International Caries Detection and Assessment System (ICDAS) employs an evidence-based and preventively oriented approach, it is a detection and assessment system classifying stages of the caries process by using visual surface characteristics to measure surface changes and potential histologic depths of caries lesions. The classification criteria, and associated estimates of caries activity, are based on the histological extension of lesions into tooth structure. The scores are on a 7-point rating scale (Young et al., 2015).

Minimal intervention dentistry (MID) is a philosophy of dental care that aims to keep teeth healthy and functional throughout a person's life. It recommends preserving not only sound tooth tissues but also tissues with the potential to remineralize so as to maximize the healing potential of the tooth (Jiang et al., 2021).

Atraumatic restorative treatment (ART) is a minimally invasive approach for the management of cavitated lesions. The ART procedure involves removal of soft carious dental tissues using hand instruments without giving local anesthesia and placement of restoration using adhesive dental material, mostly high viscosity glass ionomer cement (GIC) which provides chemical adhesion to the tooth surface, fluoride release, and biocompatibility (Jiang et al., 2021).

Glass Ionomer Cement used in ART is considered as a satisfactory option for treatment of decayed primary teeth in young ages and a source of fluoride release which may help in arresting caries and preventing the development of new ones and it's acceptable from the child and parents due to its white color (Duangth et al., 2017).

Silver diamine fluoride (SDF) consists of 25% silver, 5% fluoride, and 8% ammonia. SDF can arrest the caries progression and simultaneously prevent the formation of new lesions. This affordable topical solution's effectiveness is due to a combined action of remineralization aided by fluoride, potent germicidal effect by silver nitrate, and sclerotic dentine formation by silver salt. It requires minimal training, equipment, and personnel. SDF could be used for a broad range of situations, including, but not limited to, when local or general anesthesia is not preferred, when young children do not accept dental procedures, or when it is necessary to offer a less costly or less invasive alternative and recently as a non-aerosol releasing treatment during the pandemic (Wakhlo et al, 2021). Hence its use to arrest cavitated lesions in primary teeth is supported by the American Academy of Pediatric Dentistry (AAPD)(Crystal et al.,2017).

According to an umbrella review of systematic reviews (SR) done by BaniHani, et al in 2021, results from included SRs showed that 38% SDF has a statistically significant caries arrest effect in children and that its application is more effective than other preventive management strategies including GIC for arresting dentinal caries in the primary dentition ( $p < 0.5$ ). Moreover, caries arrest rate after single application of 38% SDF ranged between 31 and 79%, whereas biannual application has significantly increased the caries arrest rate to 53 and 91% (Duangthip et al., 2015; Jabin et al., 2020) (BaniHani et al., 2021).

However, occasionally, there may be a situation where the patient will not be able to return for subsequent dental treatment. In this case, the provider has an option of placing SDF and a glass ionomer cement (GIC) restoration during the same appointment to limit access of fermentable carbohydrates and improve the chances of SDF caries arrest. This technique is called Silver Modified Atraumatic Restorative Technique (SMART). By placing SMART restorations, the bacteria are eliminated and the nutrient source for any remaining bacteria is cut off by placing a chemically sealed restoration that will arrest and remineralize the caries lesion (Alvear Fa., 2016).

In an Egyptian study conducted by Radi et al. in 2021 on 60 primary molars, the mean survival rate of SMART restorations was 11.2 months higher than that restored with ART restorations, within a follow-up period of 12 months. Although there was a statistically significant decrease in all the tested clinical criteria success rate (spontaneous pain,

mobility, sensitivity to percussion and sinus or swelling) within both groups, with ( $P$ -value <0.001, effect size = 0.367) for the group treated with ART and ( $P$ -value <0.001, effect size = 0.187) for the group treated with SMART (Radi et al., 2021).

In China, a study was conducted by Jiang et al. in 2019 on 194 children, in which 101 children received SMART and 93 received ART. At 24-month follow-up, there was no significant difference between the ART restoration success rates of the two study groups ( $p > 0.05$ ). The success rate of these restorations was affected by the class of these restorations: Class I restorations had the highest success rate (~50 %), followed by Class V (~35 %), Class II (~15 %), and Class III (<10 %). Besides, the meantime used to place SMART restorations was shorter than that in ART restorations with 4.8 and 5.1 mins respectively ( $p = 0.006$ ).

In the same study, parents were asked to rate their satisfaction with their child's teeth using a 5-point scale (5=very satisfied, 1=very dissatisfied), and the Chinese version of the Early Childhood Oral Health Impact Scale (C-ECOHIS) was used to assess the children's OHRQoL before and 6 months after the restorative treatment. At the 6-month follow-up, the mean parental satisfaction score regarding their child's dental health status increased significantly ( $p<0.001$ ) from  $2.2 \pm 0.7$  to  $2.8 \pm 1.0$  in the SMART group and from  $2.3 \pm 0.8$  to  $2.7 \pm 0.9$  in the ART group. However, no significant changes ( $p>0.05$ ) in C-ECOHIS scores were found in either of the two groups after ART restoration placement (Jiang M et al., 2019).

There is a lack of clinical trials comparing ART and SMART restorations. Thus, it is suggested to compare the clinical outcome of both techniques and their impact on oral health related quality of life in preschool children.

## **The Null Hypothesis**

There is no difference between SMART and ART in arresting caries, success, and retention rate as well as their impact on the oral health-related quality of life.

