### Secondary Aim

- To describe the change in oral health-related quality of life of preschool children before and after placement of ART and SMART restorations.

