## **Materials and Methods**

### **Study design:**

Randomized clinical trial using split-mouth design technique.

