### **Study Sampling:**

#### **• Size formula**

The sample size was specified by using the G power test, assuming a statistical level of significance of 5% and power 80% with normal distribution, and 0.367 effect size calculated from means and standard deviation of 2 groups obtained from a previous study (Jiang et al., 2021). The original sample size will be 64 molars, and will be increased up to 80 with a possible dropout.

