#### **• Randomization**

Teeth will be randomly assigned to receive either SMART or ART technique, using a website (<https://randomization.com/>)

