#### **• Grouping**

- **Group A** the teeth will be restored by ART using high viscosity glass ionomer cement (GC Fuji IX )
- **Group B** the teeth will be treated with silver diamine fluoride 38%, and then restored by high viscosity Glass Ionomer cement (Fuji IX), both according to manufacturer instructions.

- **Inclusion Criteria:**

- Generally healthy children of ages 3 to 6 years old, who have at least 2 bilateral decayed primary molars with occluso-proximal carious dentin lesions (scores 4 or 5) according to the International Caries Detection and Assessment System (ICDAS II)
- Children with negative (Rating 2) and positive (Rating 3) behavior, according to Frankel's behavior rating scale

- **Exclusion Criteria:**

- Children with systemic diseases/conditions
- Children with definitely positive and negative behavior
- Teeth with signs of pulpal pathology (abscess, fistula, mobility)
- Teeth with very deep cavities
- Teeth with signs of irreversible pulpitis

- **Ethical Approval:**

Written informed consent should be signed by patients' parents before participation in the study.

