## **II-Baseline and 6 months Assessment of ORQoL**

The Early Childhood Oral Health Impact Scale (ECOHIS) scales measures the Oral Health-Related Quality of Life (OHRQoL) of preschool children and their families. It consists of 13 items, covering six domains in two sections (Table 1). The child's impacts section contains 4 domains: symptom (1 item), function (4 items), psychology (2 items) and self-image and social interaction (2 items). The family's impacts section contains 2 domains: parental distress (2 items) and family function (2 items). The response categories for each question are rated on a 5-point Likert scale to record how often an event has occurred during the child's life: 0 = never, 1 = hardly ever, 2 = occasionally, 3 = often, 4 = very often, and 5 = don't know (Pahel et al.,2007).

The English version of the ECOHIS was translated into Arabic using the well-recognized forward-backward translation technique. As with the English version, response options for Arabic Early Childhood Oral Health Scale (A-ECOHIS) (Table 2) are rated on a 5-point Likert scale as follows: 0 = never, 1 = hardly ever, 2 = occasionally, 3 = often, 4 = very often, and 5 = don't know (Farsi et al.,2017).

At baseline, parents will be asked to complete a questionnaire that consists of the Arabic version of Early Childhood Oral Health Scale (A-ECOHIS) (Table 2). After a 6- month follow-up period, parents will be assessed and asked to complete the same form of the baseline questionnaire.

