**Table 1**

		Never 0	Hardly Ever 1	Occasionally 2	Often 3	Very Often 4	Don't Know 5
Child impact	How often has your child, because of dental problems or the need for dental treatment:						
	1) ...had pain in the teeth, mouth or jaws?						
	2) ...had difficulty drinking hot or cold beverages?						
	3) ...had difficulty to chew food?						
	4) ...had difficulty for pronouncing any words?						
	5) ...Missed pre-school or day-care?						
	6) ...had difficulty sleeping?						
	7) ...been annoyed or bad-tempered?						
	8) ...avoided laughing or smiling when around other children?						
	9) ...avoided talking?						
Family impact	How often have you or another family member, due to dental problems or dental treatment of your child:						
	10) ...felt upset?						
	11) ...felt guilty?						
	12) ...had to take hours or days off work?						
	13) ...had the family's economic situation affected?						

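### The null hypothesis includes a SMART-versus-ART difference in quality of life, but in a split-mouth trial each child has one ECOHIS change score shared by both techniques, so that clause cannot be tested

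*Combined protocol and SAP*

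**What the plan says.** The Null Hypothesis section sets out a single between-technique null covering caries arrest, success and retention, "as well as their impact on the oral health-related quality of life". The last sentence of the Introduction has the same comparative intent.

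The design and measurement sections say:

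- Study design: "Randomized clinical trial using split-mouth design technique".
- Randomization: "Teeth will be randomly assigned to receive either SMART or ART technique".
- Inclusion criteria (under Grouping): children "who have at least 2 bilateral decayed primary molars".
- Assessment of ORQoL: parents fill in the Arabic ECOHIS at baseline, and at 6 months "parents will be assessed and asked to complete the same form of the baseline questionnaire".
- Table 1: the child items open with "How often has your child, because of dental problems or the need for dental treatment", and the family items ask about the parent or another family member. No item names a tooth or a side.

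Three other sections treat quality of life differently from the null. The Primary Aim limits the SMART-versus-ART comparison to success, retention and caries arrest. The Secondary Aim is "To describe the change in oral health-related quality of life of preschool children before and after placement of ART and SMART restorations". Statistical Analysis assigns ECOHIS a paired t-test of baseline against post-intervention scores and names no ECOHIS comparison between techniques.

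**The concern.** A hypothesis about a difference between techniques needs an outcome that can differ between techniques. Restoration success can, because it is scored tooth by tooth. The ECOHIS score cannot when the same child carries both kinds of restoration: any improvement or deterioration the parent reports reflects both, together with everything else that happened to the child over 6 months.

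The risk lies in the report. The only ECOHIS test planned is the before-after paired t-test. Read against the null as written, a significant result could be presented as rejecting equal quality-of-life impact of SMART and ART, and a non-significant one as supporting it. Neither follows, because the test concerns change over time after both techniques. Quality of life is also in the trial's title, so readers will look for this conclusion.

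**Working it through.** **1. Inputs.** From the documents: split-mouth design, teeth randomized, at least two bilateral molars per child, one child-and-family questionnaire at each of two time points, and a sample size given only in molars ("The original sample size will be 64 molars, and will be increased up to 80 with a possible dropout"). The number of children is not stated, so molars per child is my assumption (two or four).

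**2. The plan's own figures.** The step from 64 to 80 corresponds to 20% dropout: 64 / (1 − 0.20) = 80. The plan gives no sample size or precision for ECOHIS, so there is no ECOHIS figure to reproduce. The point does not depend on how the 64 was obtained.

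**3. Children.** Two molars each: 64/2 = 32 and 80/2 = 40. Four molars each: 64/4 = 16 and 80/4 = 20. Each child contributes one ECOHIS change score.

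**4. Estimability.** Model the change score of child i as

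change_i = a + b_S × (number of SMART molars) + b_A × (number of ART molars) + error.

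With equal counts k_i of each technique in a child, the child's row of the design matrix is (1, k_i, k_i).

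- All children with the same number of pairs: all rows are identical, so the rank is 1 of 3.
- Children with differing numbers of pairs (for illustration, 24 with one pair and 8 with two, giving 24×2 + 8×4 = 80 molars in 32 children): the rank is 2 of 3.

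The contrast of interest, b_S − b_A, is the vector (0, 1, −1). Any combination of the rows has equal second and third entries, and this vector does not. It lies outside the row space in both cases, so b_S − b_A is not estimable. More children add more rows of the same form and do not help.

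**5. What can be estimated.** The pooled mean change. Its 95% CI half-width, in SDs of the change score, is t(0.975, n−1)/√n:

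| Children | Half-width (SD of change) |
|---|---|
| 32 | 0.361 |
| 40 | 0.320 |
| 16 | 0.533 |
| 20 | 0.468 |

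**6. The cited precedent.** The Chinese study described just before the closing rationale of the Introduction treated 101 children with SMART and 93 with ART: 101 + 93 = 194, its full sample. Each child had one technique, so ECOHIS could be reported by group there. That does not carry over to a split-mouth trial.

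**The case against.** **The plan already treats quality of life as descriptive.** The Primary Aim, Secondary Aim and Statistical Analysis all fit the design, and no endpoint, sample size or data collection step rests on the disputed clause. This is true. It limits the consequence, and it is why the correction is small. But the null is the statement a report will accept or reject, and one of its clauses has neither data nor a test behind it.

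**Non-estimability needs both techniques, in equal number, within each child.** The Randomization section does not state within-child allocation, and a child with three eligible molars could have a 2:1 split. If two teeth per child were allocated independently, the chance of both receiving the same technique is 2 × 0.5² = 0.5, so about 16 of 32 children would have one technique only and a weak between-child contrast would exist. The condition is real and should be stated. However, independent allocation would contradict the split-mouth label, and unequal counts would give only an incidental contrast for which no score or test is defined. Even a full split of 32 children into 16 per technique would have about 18% power at a standardized difference of 0.367 (the plan's effect size, borrowed only for illustration): Φ(0.367 × √(16/2) − 1.96) = Φ(−0.92) ≈ 0.18.

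**Fisher's exact test is planned for outcomes between ART and SMART.** It needs a categorical result for each technique. ECOHIS supplies one score per child, and the plan assigns it to the paired t-test.

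**Statistical Analysis is written in the past tense.** Data may already have been examined, and silently removing a hypothesis would then be poor practice. This stands, and it affects how the fix should be made.

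**Conclusion.** The concern holds. On the split-mouth reading, with equal numbers of SMART and ART molars in each child, the quality-of-life clause of the null cannot be tested at any sample size. No analysis in the plan addresses it under any reading. The ECOHIS data support one uncontrolled before-after mean change, with a precision of roughly 0.3 to 0.5 SD depending on the assumed molars per child. That precision describes the estimate that remains; it does not measure the defect, which is structural. The primary outcome and the tooth-level comparisons are not affected. The point should be fixed before results are reported.

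**What to change.** - **Null Hypothesis:** delete the quality-of-life clause, leaving no difference between SMART and ART in caries arrest, success and retention. Because the analysis section is in the past tense, record this as a dated amendment that gives the reason.
- **Introduction, last sentence:** align it, so that clinical outcomes are compared between techniques and quality of life is described.
- **Secondary Aim:** keep it, and specify the child-level change in A-ECOHIS from baseline to 6 months after care that includes both techniques.
- **Statistical Analysis:** keep the paired t-test. Report the mean change with its 95% CI and the number of children analysed, and state that it is uncontrolled and supports neither a SMART-versus-ART comparison nor a causal attribution.

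The cost is wording in four places. Sample size, randomization, data collection and the planned test stay as they are. The sponsor gives up a quality-of-life comparison that this design cannot provide; obtaining one would need children randomized to a single technique.

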## Aim of the Study

### Primary Aim

This study aims to evaluate and compare the clinical outcomes of **Silver-Modified Atraumatic Restorative Treatment (SMART)** and conventional **Atraumatic Restorative Treatment (ART)** in the management of carious primary molars in preschool children. This comparison includes:

- **Success rate:** which include restoration integrity, marginal adaptation, absence of secondary caries, and tooth vitality.
- **Retention rate:** Determined by monitoring whether the restoration remains fully or partially retained over time
- **Caries arrest:** where arrested lesions present with hard, darkened surfaces and no progression in lesion size

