## **Outcome Measurements:**

The primary outcome measure in this clinical study is the success of the ART restorations placed. The children will be examined 6 months after placement of ART restorations (Jiang et al., 2016).

The same instruments used in the baseline examination will be used in the follow-up examinations. The status of the restorations and restored teeth will be assessed and recorded using codes and criteria commonly adopted in previous clinical studies of ART restorations (Lo et al., 2007).

0 = restoration present, no caries, no marginal defects, or wear

1 = restoration present, no active caries, slight defects or wear not greater than 0.5 mm

2 = restoration present, marginal defects greater than 0.5 mm

3 = restoration present, wear greater than 0.5 mm

4 = restoration present, active caries found associated with the filling

5 = restoration missing, no active caries, surface hard to gentle probing

6 = restoration missing, active caries found, surface soft to probing allowing penetration of the tip of a blunt probe

7 = tooth with signs of pulpal pathology

8 = tooth missing, extracted due to caries

9 = tooth naturally exfoliate

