## **Statistical Analysis:**

Data analysis was carried out by using the statistical software SPSS (version 28, IBM SPSS statistics, USA. Based on the results of the Shapiro-Wilk test, most of the data were determined to follow a normal distribution. The significance level was set at  $p \leq 0.05$ . The qualitative data were presented as frequencies and percentages, whereas the quantitative data were presented as median, range, mean, and standard deviation values. Paired Samples

t-Test was used to compare the means of two related groups, it was used to assess changes in ECOHIS scores at baseline and after intervention. Fishers exact test was used to compare the outcomes between ART and SMART at a single time point. Categorical data like the relation between the success rate of both treatments and the type of the cavity was analyzed by using the Chi-Square Test of Independence. The significance level was set at  $p \leq 0.05$ .

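### The Null Hypothesis and Primary Aim do not match the single primary outcome named in Outcome Measurements, and three clinical outcomes are tested at 0.05 with no order or adjustment

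*Combined protocol and SAP*

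**What the plan says.** Four sections of the combined protocol and SAP bear on which result decides the trial.

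- **The Null Hypothesis** is a single statement: "There is no difference between SMART and ART in arresting caries, success, and retention rate as well as their impact" on oral health-related quality of life. It has four components.
- **Primary Aim** describes comparing SMART with ART in the "management of carious primary molars in preschool children. This comparison includes" success rate, retention rate and caries arrest. Three outcomes are listed and none is ranked. The Secondary Aim contains only a description of change in quality of life.
- **Outcome Measurements** names one: "The primary outcome measure in this clinical study is the success of the ART restorations placed", with examination 6 months after placement.
- **Statistical Analysis** says: "Fishers exact test was used to compare the outcomes between ART and SMART at a single time point". It sets p ≤ 0.05 twice ("The significance level was set at" that value). It gives no testing order, no division of the 5% and no adjustment. ECOHIS gets a paired t-test of baseline against follow-up.

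The sample size paragraph (Size formula) is for one unnamed comparison, "assuming a statistical level of significance of 5% and power 80% with normal distribution".

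**The concern.** The sections give three different answers to the question of what the trial must show: four components, three outcomes or one. Outcome Measurements does not call retention and caries arrest secondary. The Primary Aim calls them primary, and the Secondary Aim leaves them out. Their status is therefore open.

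Two things follow. First, a difference confined to retention or to caries arrest could be presented as meeting the primary aim or rejecting the null hypothesis, and the text would allow it. The error rate for that claim is that of three tests, not one. Second, the headline outcome could be settled after the results are known. A reader of the trial report could not tell from this plan whether that had happened.

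**Working it through.** **1. Does the planned size allow for more than one test?** Inputs from Size formula: 5% significance, 80% power, "0.367 effect size calculated from means and standard deviation of 2 groups obtained from a previous study", and "The original sample size will be 64 molars, and will be increased up to 80 with a possible dropout". The type of effect size is not named, and two-sided testing is assumed. Using the full 5% for one comparison:

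| Reading of 0.367 | Required number |
|---|---|
| Chi-square, w | 59 in total |
| Two-group comparison, f | 62 in total |
| Paired t-test | 61 pairs |
| Wilcoxon signed-rank | 64 pairs |
| Two-sample t-test, d | 118 per arm |

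The first four readings at 0.05/3 = 0.0167 need 78 to 85. None of the calculations tried at the divided level gives 64. The dropout step is 64/0.80 = 80. The choice among the readings is a separate question. What matters here is that nothing in the paragraph divides the 5%.

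**2. How many between-arm tests?** Success, retention and caries arrest make three. The planned ECOHIS test is before against after, not ART against SMART, so it is not counted.

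**3. Three independent tests, each exactly 5%.** 1 − 0.95³ = 1 − 0.857 = 0.143, or 14.3%.

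**4. Allowing for correlation between outcomes.** Three simulated two-sided z-tests with equal correlation gave 12.6% at 0.5, 10.9% at 0.7 and 8.3% at 0.9. The documents give no correlation, so this is a range.

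**5. The planned Fisher test on independent teeth.** Fisher's test is conservative at this size. With 32 or 40 teeth per arm and a common event rate from 0.15 to 0.85, its true size is between 1.91% and 3.30%. Three independent outcomes then give from 1 − (1 − 0.0191)³ = 5.6% to 1 − (1 − 0.0330)³ = 9.6%.

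**6. The planned Fisher test on split-mouth data.** Assumptions: no treatment difference, outcome rates of 60%, 75% and 70%, a latent-normal model and 12,000 replicates. The chance of at least one p ≤ 0.05 was:

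| Pairs | Correlation between outcomes | Within-child correlation 0 | Within-child correlation 0.3 |
|---|---|---|---|
| 32 | 0 | 8.3% | 4.5% |
| 32 | 0.5 | 8.0% | 4.4% |
| 32 | 0.8 | 7.2% | 4.3% |
| 40 | 0 | 8.7% | 4.6% |
| 40 | 0.5 | 8.3% | 4.6% |
| 40 | 0.8 | 7.6% | 4.5% |

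The drop from the third column to the fourth is the effect of analysing pairs as if they were independent.

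**7. All three outcomes read from the restoration codes.** Assumed mapping: success = codes 0-1, retention = codes 0-4, arrest = codes 0-3 and 5. Several code distributions were assumed, with 32 and 40 pairs. The documents give neither the mapping nor the distributions. The chance of at least one false positive was:

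- mid-p McNemar: about 10-12%
- exact McNemar: about 5-8%, with one set of runs as low as 4.5%
- planned Fisher test: about 6-8% at zero within-child correlation and about 2.5-6% at 0.2 to 0.4

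**The case against.** The strongest reply is that Outcome Measurements settles the matter. It names a single primary outcome with one time point. The Primary Aim only lists what a comparison covers, and the null hypothesis can be read as shorthand for separate nulls, since no global test is planned. This stands in part: if that section governs, the 5% level for success is intact. But the plan does not say that it governs, and the section headed Primary Aim still gives retention and arrest equal standing.

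The second reply concerns size, and most of it stands. A reader might infer that the stated 5% is broken under the plan as written. The documents do not support that. With the planned Fisher test and a within-child correlation of 0.2 to 0.4, the rate for three outcomes is about 2.5-6%, mostly below 5%. This protection is accidental, since it comes from ignoring the pairing, and a paired analysis would remove it.

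A reader might also count four outcomes and quote 1 − 0.95⁴ = 18.5%. That fails. Quality of life is a descriptive secondary aim. One parental questionnaire per child cannot separate two techniques used in the same mouth, and no between-arm test is planned for it.

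Finally, the code mapping in step 7 is an assumption. The Primary Aim defines arrest partly by darkening and lesion size, which the codes do not record.

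**Conclusion.** The inconsistency is in the text and should be corrected. As written, a significant result on any one of three clinical outcomes could be claimed as meeting the primary aim, with no rule against choosing among them.

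The size is modest and rests on assumptions. The 14.3% figure is the reference value for independent, exact tests and should not be quoted as the trial's error rate. The plausible ranges come from assumed outcome distributions and correlations, because the documents supply none. They reach above 5% for both paired tests and lie on either side of it for the planned Fisher test. A breach of 5% under the plan's own test is therefore not shown. The case for change rests on the conflict between sections and the open choice of headline outcome. Severity is minor to moderate.

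**What to change.** Reword The Null Hypothesis and Primary Aim to agree with Outcome Measurements, so that success at 6 months is the only confirmatory outcome, tested at 0.05. Label retention, caries arrest and ECOHIS as secondary. Report retention and arrest as between-arm differences with confidence intervals, and ECOHIS as before-after change with its interval, with no confirmatory claim for any of them. Add one sentence to Statistical Analysis saying so.

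The cost is a few sentences. The figure of 64 molars needs no change on account of multiplicity, because it already gives the full 5% to one comparison. The one real loss is that a difference in retention or arrest alone could no longer carry the trial's main conclusion.

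If all three clinical outcomes must stay primary, Holm's method would control the error rate, but this is not just a wording change. At its first step (0.0167), power at 64 falls from 81-84% to 66-71% across the first four readings in step 1. Restoring 80% takes 78 to 85 instead of 59 to 64, before dropout.
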